6.5. RETESTS, UNSCHEDULED VISITS AND EARLY TERMINATION DATA

In general, for by-visit summaries, data recorded at the nominal visit will be presented. Unscheduled measurements will not be included in by-visit summaries but will contribute to the best/ worst case value where required (e.g. shift table).

In the case of a retest (same visit number assigned), the latest available measurement for that visit will be used for by-visit summaries

Listings will include scheduled, unscheduled, retest and early discontinuation data.

6.6. WINDOWING CONVENTIONS

There will be no visit windowing for these analyses. All data will be organized and analyzed according to the scheduled times as outlined in the protocol and by the visit denoted on the Case Report Form (CRF).

6.7. STATISTICAL TESTS

No statistical tests will be performed.

Unless otherwise specified in the description of the analyses, two-sided 95% s will be used.

6.8. COMMON CALCULATIONS

- For quantitative measurements, change from baseline will be calculated as:

Document:	Roche_YP40902_SAP	Version Number:	2.2
Authors:	[REDACTED], [REDACTED], [REDACTED]	Version Date:	06MAR2020
Template No.:	CS_TP_BS016 Revision 5	Reference:	CS_WI_BS005
Effective Date:	01April2018		

Test Value at Visit X – Baseline Value

- Percent change from baseline will be calculated as:
$$(\text{Test Value at Visit X} - \text{Baseline Value})/\text{Baseline Value} *100$$
- The time from Date of Event A to Date of Event B (days) is calculated as:
$$(\text{Date of Event B} - \text{Date of Event A} + 1)/365.25$$
- The time from Date of Event A to Date of Event B (months) is calculated as:
$$(\text{Date of Event B} - \text{Date of Event A} + 1)/30.4375$$
- The time from Date of Event A to Date of Event B (weeks) is calculated as:
$$(\text{Date of Event B} - \text{Date of Event A} + 1)/7$$

6.9. SOFTWARE VERSION

All derivations, statistical analyses, summaries, and listings will be generated using SAS version 9.4 or higher (SAS Institute, Inc., Cary, North Carolina). Noncompartmental PK parameter calculations will be performed using Phoenix® WinNonlin® 8.0 or higher (Certara, L.P., Princeton, New Jersey, United States). Graphics will be prepared using the same version of SAS.

7. STATISTICAL CONSIDERATIONS

7.1. ADJUSTMENTS FOR COVARIATES AND FACTORS TO BE INCLUDED IN ANALYSES

There will be no adjustment for covariates in these analyses.

7.2. MULTICENTER STUDIES

This study will be conducted at one site. Center pooling is not applicable for use in analyses for this study.

7.3. MISSING DATA

For identification of previous or concomitant medications/non-drug treatment, no formal imputation will be performed on missing or incomplete dates. Rules presented in Appendix 2 [Table 2](#) will be used to define if a medication/non-drug treatment is considered as a previous, concomitant or both previous and concomitant

Document: Roche_YP40902_SAP

Authors: [REDACTED], [REDACTED], [REDACTED]

Version Number: 2.2

Version Date: 06MAR2020

Template No.: CS_TP_BS016 Revision 5

Reference: CS_WI_BS005

Effective Date: 01April2018

medication/non-drug treatment.

8. OUTPUT PRESENTATIONS

[Appendix 1](#) shows conventions for presentation of data in outputs.

The templates provided with this SAP describe the presentations for this study and therefore the format and content of the summary tables, figures, and listings to be provided by [REDACTED] Biostatistics.

9. SCREEN FAILURE

This study will list or summarize the category and reasons in table and listings for the patients who experience screen failure. All patients who signed informed consent form (ENR) will be analyzed.

10. DISPOSITION AND WITHDRAWALS

All subjects who are randomized will be accounted for in this study.

Subject disposition and withdrawals will be presented for the RND set.

Following summaries will be produced by dose group:

- Subjects randomized
- Subjects randomized but not treated
- Subjects treated
- Subject who completed the study
- Subject who discontinued the study and reasons

11. PROTOCOL DEVIATIONS

Protocol deviation will be collected by clinical team and entered into clinical trial management system (CTMS). The major protocol deviation will be tabulated by dose group. All protocol deviations will be presented in listing including category, term, PD date, and severity for SAF. The categories of protocol deviation may include:

- Informed Consent Criteria
- Eligibility and Entry Criteria
- Concomitant Medication Criteria

Document: Roche_YP40902_SAP

Authors: [REDACTED], [REDACTED], [REDACTED]

Version Number: 2.2

Version Date: 06MAR2020

Template No.: CS_TP_BS016 Revision 5

Reference: CS_WI_BS005

Effective Date: 01April2018

- Laboratory Assessment Criteria
- Study Procedures Criteria
- Serious Adverse Event Criteria
- Visit Schedule Criteria
- IP Compliance
- Administrative Criteria
- Source Document Criteria
- Regulatory or Ethics Approvals Criteria
- Other Criteria

12. DEMOGRAPHIC AND OTHER BASELINE CHARACTERISTICS

Demographic data and other baseline characteristics will be presented for the SAF by dose group.

No statistical testing will be carried out for demographic or other baseline characteristics.

The following demographic and other baseline characteristics will be reported for this study:

- Age (years) - calculated relative to date of consent
- Sex
- Ethnicity
- Race
- Weight (kg)
- Height (cm)
- BMI (kg/m²)
- Breath Alcohol Test
- Urine Cotinine Test
- Urine Drug Screen

12.1. DERIVATIONS

- BMI (kg/ m²) = weight (kg)/ height (m)²
- Age (Years) = (Date of Informed Consent – Date of Birth+1)/365.25

Document: Roche_YP40902_SAP

Authors: [REDACTED], [REDACTED], [REDACTED]

Version Number: 2.2

Version Date: 06MAR2020

Reference: CS_WI_BS005

Template No.: CS_TP_BS016 Revision 5

Effective Date: 01April2018

[REDACTED]

13. MEDICAL HISTORY

Medical History information will be presented for the SAF by dose group.

All medical history from eCRF page 'Medical History' will be coded with Medical Dictionary for Regulatory Activities (MedDRA) central coding dictionary, Version 22.0 (MedDRA v22.0) or higher and will be summarized by system organ class (SOC) and preferred term (PT) for SAF. Number of subjects and percentage to the analysis set will be presented in frequency tables, ordered by primary SOC and PT in descending order of the frequency in group. For SOCs or PTs with the same frequency in group, categories will be sorted alphabetically.

14. PRIOR AND CONCOMITANT MEDICATIONS/ NON-DRUG TREATMENT

Medications will be presented for the SAF and coded using WHO Drug Dictionary Global version 01MAR2019. Medications will be presented by PT for the SAF.

Non-Drug treatments will be and coded using MedDRA v22.0 and presented by SOC and PT for the SAF.

See [Appendix 2](#) for handling of partial dates for medications/non-drug treatments, in the case where it is not possible to define a medication/non-drug treatment as prior or concomitant, the medication/non-drug treatment will be classified as concomitant.

- 'Prior' medications/ non-drug treatments are these which started and stopped prior to the first dose of study medication.
- 'Concomitant' medication/non-drug treatments are these which:
 - started prior to, on or after the first dose of study medication
 - AND ended on or after the date of first dose of study medication or were ongoing at the end of the study.

15. STUDY MEDICATION EXPOSURE AND COMPLIANCE

The date of study medication administration will be taken from the eCRF 'Drug Administration' form. Study medication administration will be tabulated and listed by group for SAF.

Missing or partial dates or time for study medication administration will not be imputed.

Document: Roche_YP40902_SAP

Authors: [REDACTED], [REDACTED], [REDACTED]

Version Number: 2.2

Version Date: 06MAR2020

Template No.: CS_TP_BS016 Revision 5

Reference: CS_WI_BS005

Effective Date: 01April2018

[REDACTED]

16. PHARMACOKINETIC ANALYSIS

16.1. PLASMA CONCENTRATION DATA

Individual PK blood sample collection times, derived sampling time deviations, and plasma concentrations of baloxavir marboxil and its metabolite will be listed.

Plasma concentrations for baloxavir marboxil and its major metabolite, baloxavir, will be summarized using descriptive statistics for each dose level by scheduled time, as described in [Section 6.1](#). Concentrations that are below the limit of quantitation (BLQ) will be treated as zero for the computation of descriptive statistics, except for the calculation of geometric mean where BLQ values will be set to $\frac{1}{2}$ of the lower limit of quantitation (LLOQ). Concentrations that are missing will be omitted from the calculation of descriptive statistics.

For each analyte, figures of overlaid arithmetic mean concentration-time profiles at each dose level will be presented. Individual subject concentration-time profiles grouped by dose (all profiles presented in one plot) and by-subject plots displaying on the same graph profiles for both analytes (one plot for each subject) will also be presented. All concentration-time profiles will be depicted on linear and semi-logarithmic scales.

16.2. PLASMA PHARMACOKINETIC PARAMETERS

Single-dose PK parameters for plasma baloxavir marboxil and its major metabolite, baloxavir, will be estimated by noncompartmental methods using actual elapsed time from dose administration in the final analysis. Subjects with partial data will be evaluated on a case-by-case basis to determine if sufficient data are available for reliable estimation of PK parameters.

The following data handling conventions for concentrations apply to the PK analysis:

- Pre-dose samples that are missing or BLQ will be assigned a numerical value of zero.
- Any pre-dose concentration values that are quantifiable will be included in the PK analysis. Concentrations and the calculated PK parameters shall be listed and included in the applicable summaries and inferential statistics. Profiles with anomalous pre-dose concentration value which is not greater than 5% of C_{max} will be evaluated. The presence of anomalous pre-dose concentration value greater than 5% of C_{max} in the profile will be evaluated on a case-by-case basis to determine if exclusion is warranted by the data.

Document: Roche_YP40902_SAP

Authors: [REDACTED], [REDACTED], [REDACTED]

Version Number: 2.2

Version Date: 06MAR2020

Template No.: CS_TP_BS016 Revision 5

Reference: CS_WI_BS005

Effective Date: 01Apr2018

F. Hoffmann-La Roche Ltd and Shionogi & Co., Ltd
PROTOCOL YP40902

Statistical Analysis Plan

Page 19 of 31

- Post-dose BLQ concentrations will be assigned a value of zero if they precede quantifiable data points in the initial portion of the profile (before C_{max}).
- A BLQ value that occurs between quantifiable data points, especially prior to C_{max} will be evaluated to determine if an assigned concentration of zero makes sense, or if reanalysis or exclusion of the data is warranted.
- Following C_{max} , BLQ values embedded between 2 quantifiable data points will be treated as missing.
- Trailing BLQ values at the end of the collection interval (after the last quantifiable concentration) will be set to zero.
- If consecutive BLQ concentrations are followed by quantifiable concentrations in the terminal portion of the concentration curve, these quantifiable values will be set to missing (blank data) and excluded from the PK analysis, unless otherwise warranted by the concentration time profile.

Handling of PK Concentration Values From Subjects Who Vomit:

- If a subject vomits at or before the 12th hour following dosing, only their PK concentration values up to the emesis event will be included in the PK concentration summary. If a subject vomits after the 12th hour following dosing, all their PK concentration values will be included in the PK concentration summary.

The molecular formula and molecular weight (MW) for each analyte are listed below:

- Baloxavir marboxil:
- Molecular Formula: $C_{27}H_{23}F_2N_3O_7S$
- Molecular Weight: 571.55 Da

- Baloxavir:
- Molecular Formula: $C_{25}H_{19}F_2N_3O_4S$
- Molecular Weight: 495.55 Da

Based on clinical PK data to date from Caucasian and Japanese subjects, baloxavir plasma concentrations have not been quantifiable in any of the collected samples. The same observation is anticipated in the current study. As such, the metabolite-to-parent exposure ratios (MRC_{max} and MRAUC_{0-inf}) will only be calculated if there is detectable

Document: Roche_YP40902_SAP

Authors: [REDACTED], [REDACTED], [REDACTED]

Version Number: 2.2

Version Date: 06MAR2020

Template No.: CS_TP_BS016 Revision 5

Reference: CS_WI_BS005

Effective Date: 01April2018

baloxavir plasma levels within the profile. MRC_{max} will be calculated if the profile contains 1 or more quantifiable baloxavir concentration; whereas a minimum of 4 quantifiable baloxavir concentrations are required for the calculation of MRAUC_{0-inf}.

The following PK parameters will be calculated for both analytes where estimable, unless otherwise indicated:

C _{max} (ng/mL)	Maximum observed plasma concentration obtained directly from the concentration versus time data.
T _{max} (h)	Time to maximum observed plasma concentration, obtained directly from the observed concentration versus time data.
AUC _{0-inf} (ng·h/mL)	Area under the concentration-time curve in plasma from zero (pre-dose) extrapolated to infinite time, extrapolated to infinity by addition of the last observed quantifiable concentration divided by the elimination rate constant: AUC _{0-last} + C _{last} /λ _z .
AUC _{0-last} (ng·h/mL)	Area under the concentration-time curve in plasma from zero (pre-dose) to the time of the last quantifiable concentration.
AUC _{0-t} (ng·h/mL)	Area under the concentration-time curve in plasma from zero (pre-dose) to time t. Time t may be chosen as the latest common time point where evaluable concentrations are available in at least 90% of participants.
λ _z (1/h)	Apparent terminal rate constant, determined by linear regression of the terminal log-linear segment concentration-time curve.
t _{1/2} (h)	Apparent terminal elimination half-life, determined as: ln2/λ _z .
CL/F (L/h)	Apparent systemic clearance after oral dosing, calculated for baloxavir marboxil only as follows: Dose/AUC _{0-inf} .
V _z /F (L)	Apparent volume of distribution following oral dosing based on the terminal phase, calculated for baloxavir marboxil only as follows: Dose/(λ _z ·AUC _{0-inf}).
C ₂₄ (ng/mL)	Observed plasma concentration at scheduled 24 hour post-dose sample.
C ₄₈ (ng/mL)	Observed plasma concentration at scheduled 48 hour post-dose sample.
C ₇₂ (ng/mL)	Observed plasma concentration at scheduled 72 hour post-dose sample.

Document: Roche_YP40902_SAP

Authors: [REDACTED], [REDACTED], [REDACTED]

Version Number: 2.2

Version Date: 06MAR2020

Reference: CS_WI_BS005

Template No.: CS_TP_BS016 Revision 5

Effective Date: 01Apr2018

MRC_{max} Mole ratio of metabolite C_{max} to parent (baloxavir marboxil) C_{max}, calculated as follows:

$$\text{MRC}_{\text{max}}: \frac{\text{baloxavir } C_{\text{max}}}{\text{baloxavir marboxil } C_{\text{max}}} \times \frac{\text{baloxavir marboxil MW}}{\text{baloxavir MW}}$$

MRAUC_{0-inf} Mole ratio of metabolite AUC_{0-inf} to parent (baloxavir marboxil) AUC_{0-inf}, calculated as follows:

$$\text{MRAUC}_{0-\text{inf}}: \frac{\text{baloxavir } AUC_{0-\text{inf}}}{\text{baloxavir marboxil } AUC_{0-\text{inf}}} \times \frac{\text{baloxavir marboxil MW}}{\text{baloxavir MW}}$$

The following PK parameters will be calculated for diagnostic purposes and listed but will not be summarized.

t_{1/2}, Interval The time interval (h) of the log-linear regression to determine λ_z

t_{1/2}, N Number of data points included in the log-linear regression analysis to determine λ_z.

Rsq Goodness of fit statistic for calculation of λ_z.

%AUC_{ex} Percentage of AUC_{0-inf} obtained by extrapolation, calculated as [(C_{last}/λ_z)/AUC_{0-inf} × 100].

Areas under the curve (AUCs) will be calculated by linear up/log down trapezoidal summation, where at least 3 quantifiable post-dose concentrations are available for AUCs. If the %AUC_{ex} is >30.0% of AUC_{0-inf}, then the corresponding individual subject number will be flagged with an asterisk “*” in the listing; AUC_{0-inf} and related parameters will not be included in the applicable summaries and inferential statistics.

For partial AUC (AUC_{0-t}):

- If concentration at the end of the interval is available but collection time is missing, partial AUC will be calculated using scheduled time. In this case, the partial AUC estimate will be listed only and flagged for exclusion from the summaries and inferential statistics.
- If concentration at the end of the interval is the first BLQ value, partial AUC will be calculated (i.e. represents AUC_{all}). If concentration at the end of the interval is a later consecutive BLQ value, the partial AUC will not be calculated.

Visual assessment will be used to identify the terminal log-linear segment of the concentration-time curve for λ_z calculation. A minimum of 3 data points will be used for determination. If Rsq <0.800, λ_z and related parameters will be listed only.

The nominal dose (e.g., 40 mg or 80 mg) will be used for calculation of baloxavir marboxil dose-dependent PK parameters (CL/F and V_z/F).

For each analyte, individual PK parameters will be listed and summarized by dose levels using descriptive statistics, as described in [Section 6.1](#).

Document: Roche_YP40902_SAP

Authors: [REDACTED], [REDACTED], [REDACTED]

Version Number: 2.2

Version Date: 06MAR2020

Template No.: CS_TP_BS016 Revision 5

Reference: CS_WI_BS005

Effective Date: 01Apr2018

[REDACTED]

F. Hoffmann-La Roche Ltd and Shionogi & Co., Ltd
PROTOCOL YP40902

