## **2.2 BACKGROUND**

Baloxavir marboxil is an anti-influenza virus drug with a novel mechanism of action. Baloxavir marboxil selectively inhibits CEN activity necessary for replication of influenza viruses. A broad spectrum of activity against seasonal influenza viruses and alleviating effects on the influenza symptoms were shown in nonclinical efficacy studies and the clinical studies in patients with influenza including the Phase II proof of concept and dose finding study, the Phase III double-blind study in otherwise healthy patients, and the Phase III open-label study in otherwise healthy pediatric patients.

The novel mechanism of action of baloxavir marboxil is anticipated to be effective against influenza virus strains resistant to currently marketed drugs.

After oral administration, baloxavir marboxil is extensively converted to its active metabolite, baloxavir, predominantly by arylacetamide deacetylase in the gastrointestinal lumen, intestinal epithelium, and liver. In the dose range studied (6 mg to 80 mg), the

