maximum plasma concentration ( $C_{max}$ ) and area under the plasma concentration-time curve (AUC) of baloxavir increased generally in a dose-proportional manner. Following a single oral administration of baloxavir marboxil, the time to the maximum plasma concentration ( $T_{max}$ ) of baloxavir was reached at 4 hours, and the elimination half-life was 79.1 hours. Although the absolute bioavailability of baloxavir marboxil/baloxavir has not been established, the absorption of the drug was estimated to be good based on the total recovery of 80.1% of the administered radioactivity in feces and more than 60% was recovered post 48 hours after dosing in the  $^{14}C$  mass balance study. A food-effect study involving administration of baloxavir marboxil to healthy volunteers under fasted state and with a meal (approximately 400 to 500 kcal including 150 kcal from fat) indicated that the  $C_{max}$  and AUC of baloxavir were decreased by 48% and 36%, respectively, under fed conditions. The  $T_{max}$  was unchanged in the presence of food. Baloxavir showed serum protein-binding of 92.9% to 93.9%. The drug has multiple elimination pathways including UGT1A3 (the major pathway), and CYP3A4 (the minor pathway). In addition, the drug has an intestinal/biliary secretion, and a renal excretion (in urine, 3.3% of the administered dose was excreted as baloxavir). In vitro and in vivo human studies have shown that there is no clinically relevant effect of baloxavir marboxil and baloxavir on other co-administered medicines. There were no clinically relevant effects of other drugs (probenecid, itraconazole, oseltamivir phosphate) on the  $C_{max}$  and AUC of baloxavir.

A population PK analysis revealed that body weight and race were significant covariates on the PK of baloxavir. Based on the population modeling, the dose of baloxavir marboxil was proposed to be 40 mg for patients weighing < 80 kg and 80 mg for patients weighing  $\geq$  80 kg and investigated in the Phase III studies.

The PK/PD analysis using Phase II and Phase III data showed that at the proposed therapeutic doses, the responses of baloxavir using the virus titers change from the baseline were at the plateau, i.e., around the maximum effect.

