3.3. CHANGES TO ANALYSIS FROM PROTOCOL

1. The all subjects randomized (RND) set is added to include all subjects provided informed consent for this study and are randomized to study medication.
2. The all subjects enrolled set (ENR) is added to include all subjects who provided informed consent for this study.

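### SAP 16.2 calls baloxavir unquantifiable against the protocol's own data, gates the metabolite ratios on the numerator, and limits CL/F and Vz/F to the prodrug without declaring it

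*SAP*

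**What the plan says.** **Quantifiability.** SAP 16.2 states that in Caucasian and Japanese subjects "baloxavir plasma concentrations have not been quantifiable in any of the collected samples", and anticipates the same result here.

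**Ratios.** The SAP presents its rule for the metabolite-to-parent ratios as following from that statement. MRCmax "will be calculated if the profile contains 1 or more quantifiable baloxavir concentration"; MRAUC0-inf needs at least four such concentrations. Both ratios are defined with baloxavir in the numerator and baloxavir marboxil in the denominator.

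**Clearance and volume.** CL/F is described as "Apparent systemic clearance after oral dosing, calculated for baloxavir marboxil only as follows" Dose/AUC0-inf. Vz/F carries the same restriction: "Apparent volume of distribution following oral dosing based on the terminal phase, calculated for baloxavir marboxil only as follows" Dose/(λz·AUC0-inf). The nominal dose "will be used for calculation of baloxavir marboxil dose-dependent PK parameters".

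**Protocol.** Section 2.2 says that "baloxavir marboxil is extensively converted to its active metabolite, baloxavir", and that Tmax "of baloxavir was reached at 4 hours, and the elimination half-life was 79.1 hours". Table 3 lists CL/F and Vz/F under a primary objective that names both analytes. Section 9.4.4 makes Cmax and AUC0-inf the primary parameters, ranks the rest secondary, and lists CL/F and Vz/F with no analyte limit.

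**Declared changes.** SAP 3.3 has two entries. One begins "The all subjects randomized (RND) set is added to include all subjects provided informed consent"; the other adds the enrolled set. Neither concerns PK.

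**The concern.** An analyte that was never quantifiable cannot have a reported Tmax, half-life, food effect or dose-proportionality result. The SAP sentence therefore appears to name the wrong compound, and it is used to justify a working rule. A trigger meant to stop ratios being attempted when one analyte is missing should test the analyte expected to be missing. This one tests the other.

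The CL/F and Vz/F restriction is a separate statement, and the documents do not show that it comes from the same slip. The two combine badly, however. If the prodrug is the unquantifiable analyte, the SAP calculates clearance and volume only where there are no data and omits them where there are. Protocol 2.2 says the Chinese PK data will be compared with Japanese and Caucasian data, so a missing summary for the measurable analyte is a real gap.

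**Working it through.** The plan gives no figure of its own to reproduce. The check compares the texts, tests the trigger, and asks whether baloxavir CL/F and Vz/F could be estimated.

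**1. The texts side by side**

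- SAP 16.2: baloxavir was not quantifiable in any sample.
- Protocol 2.2, for baloxavir: Tmax 4 h; half-life 79.1 h; Cmax and AUC roughly proportional to dose over 6 to 80 mg; Cmax and AUC lower by 48% and 36% with food; body weight and race as population-PK covariates.
- SAP 3.1 bases the sample size partly on AUC and Cmax variability seen in Caucasian and Japanese participants. Some analyte was therefore quantified in the same populations, though it is not named.

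With only two analytes, elimination points to baloxavir marboxil as the unquantifiable one. This is an inference: no LLOQ is given. The slip is local. Elsewhere SAP 16.1 and 16.2 label parent and metabolite correctly, and both ratio formulas point the right way.

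**2. The ratio trigger**

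| Case | Trigger met? | Ratio |
|---|---|---|
| Prodrug all BLQ, baloxavir quantifiable | Yes | No usable denominator |
| Baloxavir all BLQ, prodrug quantifiable | No | 0 |

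How often would it be met? Protocol Table 2 has 18 post-dose PK samples. One half-life after Tmax is 4 + 79.1 = 83.1 h. Nine samples (4, 5, 6, 8, 12, 24, 36, 48 and 72 h) fall between Tmax and that time. With mono-exponential decline, C(t)/Cmax = exp[−ln2·(t − 4)/79.1], which gives 84% at 24 h, 55% at 72 h, 24% at 168 h and 6.7% at 312 h. Four quantifiable baloxavir values should be present in almost every profile.

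**3. Could baloxavir CL/F and Vz/F be estimated?**

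Both need AUC0-inf, which the SAP drops from summaries when more than 30% is extrapolated.

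- ke = ln2/79.1 = 0.00876 per h.
- Assumption: one-compartment oral profile, with ka chosen so that Tmax is 4 h (ka = 1.249 per h).
- Extrapolated fraction at last sample time T = [ka·exp(−ke·T) − ke·exp(−ka·T)]/(ka − ke).

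| T (h) | Source | Extrapolated |
|---|---|---|
| 288 | 312 h minus the 24 h window | 8.1% |
| 312 | Day 15, Table 2 | 6.5% |
| 336 | Day 15, Table 1 | 5.3% |
| 360 | 336 h plus the 24 h window | 4.3% |

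The last sample at 312 h is 312/79.1 = 3.9 half-lives after dosing. For 30% to be extrapolated at 312 h under mono-exponential decline, the half-life would have to be ln2 × 312/(−ln 0.30) = 179.6 h, or 179.6/79.1 = 2.27 times the protocol value. Baloxavir CL/F and Vz/F are therefore absent because of the analyte restriction, not for lack of data.

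**4. Dose basis if baloxavir is added**

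The SAP molecular weights give 571.55/495.55 = 1.153. Values based on prodrug mass would be about 15% higher than values based on the molar-equivalent baloxavir dose, so the convention must be stated.

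**The case against.** The strongest reply is that this is one wrong word with little effect on the results.

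- **No wrong ratio would be printed.** The SAP calculates parameters only where estimable, and requires at least three quantifiable values for an AUC and three points for λz. This stands. The ratios are also not protocol endpoints. The defect is a trigger that does no useful work, not a false number.
- **No PK information is lost.** Baloxavir AUC0-inf is listed and summarized, and t1/2 gives λz as ln2/t1/2. With a fixed nominal dose, geometric mean CL/F equals Dose divided by geometric mean AUC0-inf, and individual CL/F and Vz/F can be worked out from the listings. This also stands. What is missing is the planned summary.
- **Limiting CL/F to the dosed compound can be defended.** Dose/AUC for a metabolite also depends on the fraction converted, and Protocol 9.4.4 applies non-compartmental analysis only where appropriate, with no instruction to report CL/F per analyte. That could be a good reason, but the SAP does not give it. The restriction still narrows an unrestricted list under a two-analyte objective and belongs in SAP 3.3.
- **The dose sentence is ambiguous.** It may mean parameters that depend on the baloxavir marboxil dose. Granted, but the CL/F and Vz/F definitions restrict the analyte by themselves.
- **The effect on the ethnic comparison is not shown.** No passage says CL/F or Vz/F will be compared. This limits the consequence.

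Protocol 2 also uses baloxavir loosely for the product. That does not rescue the sentence, because SAP 16.2 lists baloxavir just above it as a separate analyte with its own molecular weight.

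**Conclusion.** The concern holds and should be fixed. The contradiction and the undeclared restriction are certain from the text. The consequence depends on baloxavir marboxil being the unquantifiable analyte, which is likely but not stated. If so, CL/F and Vz/F are estimable in 0 of 32 participants, and baloxavir, for which about 6.5% extrapolation is expected (4.3% to 8.1% across the possible last sampling times), gets neither. The ratio trigger would pass almost every profile without protecting the denominator.

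The damage is bounded. Baloxavir Cmax, Tmax, AUCs, t1/2, C24, C48 and C72 remain planned, so the primary parameters of Protocol 9.4.4 survive. The extrapolation figures assume a one-compartment profile and the protocol half-life. The expectation that baloxavir is quantifiable in most samples rests on fractions of Cmax, since the LLOQ is not given.

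**What to change.** In the SAP:

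1. Check the quantifiability statement in 16.2 against the source PK data and correct the analyte it names.
2. Make the ratios conditional on quantifiable baloxavir marboxil: at least one value for MRCmax; at least four values and an estimable AUC0-inf for MRAUC0-inf.
3. Calculate CL/F and Vz/F for baloxavir, and for baloxavir marboxil where estimable. State whether the dose is the nominal prodrug mass or its molar equivalent, matching the convention of the Japanese and Caucasian comparison data, and reword the nominal-dose sentence to cover both analytes.
4. Record the change in 3.3. If the prodrug-only restriction is intended, keep it and give the reason there instead.

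The cost is a few lines of SAP text and a change to the non-compartmental set-up. No new samples or data are needed.
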